 - For subjects with systolic blood pressure \geq 140 mmHg **OR** diastolic blood pressure \geq 90 mmHg at **baseline** (Visit 3):
An increase, compared to baseline (Visit 3) at **2 consecutive visits**, in the average of 3 systolic blood pressures by \geq 20 mmHg **or** 3 diastolic blood pressures by \geq 10 mmHg
 - Initiation or increase in dose of medication for treatment of hypertension in any subject

Note 1: The onset date for an AESI hypertension is the first of the dates when the event meets any of the above criteria.

Note 2: An *AE of “increased blood pressure”* should be recorded if, in the investigator’s opinion, an elevated blood pressure measurement is clinically significant but does not fulfill the above definition for hypertension.

- Adverse events consistent with **orthostatic hypotension** as confirmed by orthostatic vital signs
- **Elevated serum aspartate aminotransferase (AST) or alanine aminotransferase (ALT)** lab value requiring that study drug be temporarily withheld or permanently discontinued (see [Sections 8.4.6.1](#) and [8.4.6.2](#)). To date, no concern regarding drug-induced liver toxicity has been identified; however, the Sponsor is monitoring laboratory data for a potential safety signal, consistent with Food and Drug Administration guidance [[FDA Guidance, 2009](#)].
- **Neoplasms**

Serious AESIs and elevated liver enzymes or bilirubin requiring withholding of study drug (see [Section 8.4.6.1](#)) must be reported within 24 hours of the study site personnel's knowledge of the event by marking the appropriate box on the AE eCRF and assigning the most appropriate category. Additional information should be provided as directed in the eCRF Completion Guidelines. AESIs that also meet the definition of an SAE must be reported as an SAE, as described in [Section 8.4.4](#). Nonserious AESIs should be reported within 72 hours of the site personnel's knowledge, using the AE eCRF.

8.4.6.1. Criteria for Temporary Withholding of Study Treatment in Association with Liver Test Abnormalities

Elevated liver enzymes or bilirubin sufficient to require withholding study medication must be reported **within 24 hours of the study site personnel's knowledge of the event** using AESI specific eCRFs/forms/worksheets provided for the study.

Hepatic enzymes will be monitored in accordance with FDA drug-induced liver injury guidelines [[FDA, 2009](#)].

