9.4.3.1. Adverse Events

An AE will be considered a treatment-emergent AE (TEAE) if:

- The AE began on or after the date of the first dose of study drug; or

- The AE was present before the date of the first dose of study drug, but increased in severity or became serious on or after the date of the first dose of study drug

An AE that occurs more than 5 days after the last dose of study drug will not be counted as a TEAE.

An AE will be considered a treatment-emergent SAE (TESAE) if it is a TEAE that additionally meets any SAE criteria.

AEs will be coded using the latest version of MedDRA. An overall summary table of AEs by treatment group will be presented with number and percentage of subjects. The incidence of all TEAEs by primary SOC and PT will be prepared for all TEAEs, TESAEs, treatment-related TEAEs/TESAEs, TEAEs leading to discontinuation from study treatment and all TEAEs by maximum intensity. All AEs will be listed. The number and percentage of subjects with AEs of special interest, as defined in [Section 8.4.6](#), will be summarized by treatment group.

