7.1. Adverse Events

AEs will be coded using MedDRA version 22.0 or later.

All reported AEs (whether treatment emergent or not) will be included in by-subject AE listings. Sorting will be by country, site, subject, date of event, SOC, PT and then verbatim description.

An AE will be considered treatment emergent (TEAE) if it begins or worsens in severity after the first dose of the double-blind Study Treatment through 5 days after the last dose of Study Treatment or rollover to the extension study, whichever occurs first. Partial AE start dates will be imputed as detailed in [Section 4.2.3](#).

Summary tables will be based on TEAEs. The incidence of TEAEs will be presented using counts and percentages of subjects with TEAEs and tabulated by SOC and PT. SOC will be sorted in descending frequency and PT within SOC will be sorted by descending frequency based on the incidence across subjects overall. If a subject has multiple occurrences (start and stop) of an event associated with a specific SOC or PT within a SOC, a subject will only be counted once in the incidence count for the SOC or PT within SOC respectively.

An overall summary table of AEs by treatment group will be presented detailing the number and percentage of subjects, and number of events for the following categories:

- At least one TEAE;
- At least one Treatment-Related TEAE;
- At least one Grade ≥ 3 TEAE (Mild = Grade 1, Moderate = Grade 2, Severe or Medically Significant = Grade 3, Life-Threatening = Grade 4, Death = Grade 5)
- At least one Grade ≥ 3 Treatment-Related TEAE;
- At least one Serious TEAE;
- At least one Serious Treatment-Related TEAE;
- At least one TEAE leading to Discontinuation from Study Medication;
- At least one TEAE of Special Interest;
- At least one Treatment-Related TEAE of Special Interest

Where not otherwise noted, all the following summaries are presented by PT in descending overall frequency:

- All TEAEs (by SOC and PT in descending overall frequency);
- All TEAEs (by PT in descending overall frequency)
- Treatment-Related TEAEs (i.e., possibly or probably related);
- All TEAEs by SOC, PT, and maximum severity (where the maximum intensity per patient will be counted at each level of summarization);
- TEAES with Grade ≥ 3 ;
- Treatment-Related TEAES with Grade ≥ 3 ;

- Serious TEAEs;
- Treatment-Related Serious TEAEs;
- Fatal TEAEs;
- TEAEs leading to Discontinuation from Study Treatment;
- TEAE of Special Interest;

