- Treatment-Related TEAE of Special Interest;
- Non-fatal TEAEs;
- Hypertension TEAEs by Pre-existing Hypertension (Yes vs No) and Baseline Hypertension (Yes vs. No). Hypertension TEAEs will be selected as any TEAE with preferred term of Hypertension.
- Non-serious TEAEs occurring in 2% or more of any treatment group.

In addition, a summary of all TEAEs by PT occurring in at least 2% of subjects in the vibegron arm and greater than the placebo arm will be created and sorted by descending frequency in the vibegron arm.

Adverse events of special interest for this study include:

- Adverse events consistent with urinary retention
- Adverse events suggestive of cystitis or urinary tract infection (UTI)
- Potential major cardiac and cerebrovascular events, including death (or any event with fatal outcome), myocardial infarction, cerebrovascular accident, hospitalization for unstable angina or chest pain, hospitalization for heart failure requiring hospitalization, and coronary revascularization/angioplasty/stent
- Adverse events consistent with hypertension (see protocol section 8.4.6)
- Elevated serum aspartate aminotransferase (AST) or alanine aminotransferase (ALT) lab value requiring that study drug be temporarily withheld or permanently discontinued
- Neoplasms

Treatment listings will include the treatment arm, start and stop dates of the AE, and days on study relative to the day of first dose of study treatment. A Treatment related AE is defined as an AE for which the investigator classifies the AE as being “Probably Related” or “Possibly Related” to study treatment on Adverse Event CRF. Missing relationship and severity (intensity) will be imputed per Section 4.2.3.

The following additional listings will be provided:

- Listing of deaths
- Listing of Serious TEAEs

- Listing of treatment-emergent AESIs
- Listing of TEAEs leading to withdrawal or Interruption of study treatment

Listing of all AEs with a flag for TEAEs and onset (Prior = prior to first dose of single-blind medication, Run-in = on or after first dose of single-blind medication but prior to first dose of double-blind medication, or Treatment = on or after first dose of double-blind medication.)

A listing of all medical history and pre-double-blind treatment adverse events with coded preferred terms belonging to the standard MedDRA query of hypertension will be created.

7.2. **Laboratory Evaluations**

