Title	Population	Programming notes
14.2.12.2 Overall Symptom Control over Bladder Symptoms Based on Patient Global Impression of [REDACTED] (PGI-[REDACTED])	FAS	Repeat 14.2.12.1
14.2.12.3 Overall Symptom Frequency Based on Patient Global Impression of [REDACTED] (PGI-[REDACTED])	FAS	Repeat 14.2.12.1
14.2.12.4 Overall Urgency-Related Leakage over Bladder Symptoms Based on Patient Global Impression of [REDACTED] (PGI-[REDACTED])	FAS-I	Repeat 14.2.12.1
14.2.12.5 Overall Change of Bladder Symptoms Based on Patient Global Impression of [REDACTED] (PGI-[REDACTED])	FAS	Categorical summary
14.2.12.1 [REDACTED] Domain Scores and Overall Satisfaction Score	FAS	Include CFB
Safety Endpoints		
Adverse Events		
14.3.1.1 Overall Summary of Treatment Emergent Adverse Events	SAF	
14.3.1.2 Treatment Emergent Adverse Events by System Organ Class and Preferred Term	SAF	

Title	Population	Programming notes
14.3.1.3 Treatment-Related Treatment Emergent Adverse Events by Preferred Term	SAF	
14.3.1.4 Treatment-Emergent Adverse Events by Preferred Term and Maximum Intensity	SAF	
14.3.1.5 Treatment Emergent Adverse Events with Grade ≥ 3 by Preferred Term	SAF	
14.3.1.6 Treatment-Related Emergent Adverse Events with Grade ≥ 3 by Preferred Term	SAF	
14.3.1.7 Treatment-Emergent Adverse Events occurring in $\geq 2\%$ subjects of Vibegron Arm and Greater Than the Placebo by Preferred Term	SAF	
14.3.1.8 Serious Treatment Emergent Adverse Events by Preferred Term	SAF	
14.3.1.9 Treatment-Related Serious Treatment Emergent Adverse Events by Preferred Term	SAF	
14.3.1.10 Treatment Emergent Adverse Events Leading to Discontinuation from Study Treatment by Preferred Term	SAF	
14.3.1.11 Fatal TEAEs by Preferred Term	SAF	

Title	Population	Programming notes
14.3.1.12 Treatment Emergent Adverse Events of Special Interest by Preferred Term	SAF	
14.3.1.13 Treatment-Related Treatment Emergent Adverse Events of Special Interest by Preferred Term	SAF	
14.3.1.14 Non-Fatal Treatment-Emergent Adverse Events by Preferred Term	SAF	
14.3.1.15 Hypertension Treatment Emergent Adverse Events by Preferred Term, and Pre-Existing Hypertension	SAF	
14.3.1.16 Hypertension Treatment Emergent Adverse Events by Preferred Term, and Baseline Hypertension	SAF	
14.3.1.17 Listing of Deaths	SAF	
14.3.1.18 Listing of Treatment Emergent Serious Adverse Events	SAF	
14.3.1.19 Listing of Treatment Emergent Adverse Events Leading to Withdrawal or Interruption of Study Treatment	SAF	

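### No planned table counts men per arm for each predefined AESI category; the gap matters most for the major cardiac and cerebrovascular composite

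*SAP*

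**What the plan says.** SAP Section 7.1 lists six AESI categories: urinary retention, cystitis or UTI, major cardiac and cerebrovascular events, hypertension, raised AST or ALT leading to study drug being withheld or stopped, and neoplasms. The cardiac item is a composite: "Potential major cardiac and cerebrovascular events, including death (or any event with fatal outcome), myocardial infarction, cerebrovascular accident", followed by hospitalizations for angina or chest pain and for heart failure, and by coronary revascularization.

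On layout, the same section says "Where not otherwise noted, all the following summaries are presented by PT in descending overall frequency". The output list in SAP Section 11.2.1 matches: Table 14.3.1.12 is "Treatment Emergent Adverse Events of Special Interest by Preferred Term", and Table 14.3.1.13 is its treatment-related counterpart. The overall summary adds the row "At least one TEAE of Special Interest" and a treatment-related version of it. Table 14.3.1.20 is a listing of subjects.

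The counting rule works at dictionary level: "a subject will only be counted once in the incidence count for the SOC or PT within SOC respectively".

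Protocol Section 9.4.3.1 promises, by treatment group, "The number and percentage of subjects with AEs of special interest" as Section 8.4.6 defines them. It does not say whether that count is pooled or by category.

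**The concern.** AESIs are defined as clinical categories, some with their own criteria, while the planned rows are dictionary terms. Protocol Section 2.4.2 says the AESIs were set out in advance so that each could be evaluated specifically, and the synopsis rests the trial on the particular safety needs of this population. The first safety question about a category is how many men in each arm had it.

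The planned tables answer this for all AESIs together, where a urinary infection and a myocardial infarction count alike, and for single terms. They do not answer it at the level at which the categories were defined. For a composite of uncommon events, that is the level at which an imbalance between arms would be looked for.

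**Working it through.** No figure in the plan is at issue, so the check is a comparison of passages and a bound on what the rows can show.

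**1. Every AESI output.**
- Overall summary: pooled rows, any and treatment-related. Not split by category.
- Tables 14.3.1.12 and 14.3.1.13: rows are preferred terms.
- Table 14.3.1.20: a listing, with no counts per arm.

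None has the six categories as rows, and no rule counts a man once per category.

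**2. Can a category count be rebuilt from term rows?** Let a category hold terms k = 1, 2, …, with n_k men in one arm, and let N be the men with at least one of them. Then max(n_k) ≤ N ≤ Σ n_k. The bounds meet only when a single term holds all the men.

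Illustration with assumed counts, not taken from the documents: two terms with 10 and 6 men give 10 ≤ N ≤ 16. With 544 randomized per arm, that is 10/544 = 1.8% to 16/544 = 2.9%. If both arms showed the same two rows, the category difference could lie anywhere from −6 to +6 men (6/544 = 1.1 percentage points either way).

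**3. Category by category, using Protocol Section 8.4.6.**
- *Major cardiac and cerebrovascular events.* Six listed components, hence many terms. A man with a myocardial infarction and a later heart failure admission is in two rows. Protocol Appendix 3 (Section 10.3) records the condition behind a procedure rather than the procedure, so a revascularization appears under its underlying diagnosis. As worded, the category also takes in any event with a fatal outcome, so a term alone does not show which category it was counted for. An organ-class row does not substitute, because it holds lesser events too. The count cannot be recovered.
- *Cystitis/UTI.* A UTI is recorded under fixed culture and leukocyturia criteria. Findings that miss the criteria go under other names, and symptomatic status is a separate field. Most events should fall in one term, but the category also names cystitis, so some split is possible.
- *Urinary retention.* One named event with fixed criteria; largely one row.
- *Hypertension.* The protocol names what to record, and Tables 14.3.1.15 and 14.3.1.16 use the single term Hypertension; largely readable.
- *Neoplasms.* Table 14.3.1.2 counts each man once per organ class. If the dictionary places neoplasms in one class, which the documents do not state, that row is close to the category count.
- *Liver enzymes.* Table 14.3.2.11 sets maximum ALT and AST against bilirubin. This shows related information but does not count men whose drug was withheld.

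**4. Is the category already recorded?** Protocol Section 8.4.6 has the site "assigning the most appropriate category" on the AE eCRF, in a sentence about serious AESIs and liver abnormalities requiring drug to be withheld. For nonserious AESIs it asks only for reporting on that form. The SAP names no AESI category variable.

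**The case against.** The best defence is that the plan breaks no commitment and loses little. The pooled row meets Protocol Section 9.4.3.1 as written. Three categories can largely be read from existing rows, UTI is channelled towards one term, fatal events have their own table (14.3.1.11), and a reader could count by hand from the listing. Most of this stands, and it limits the point.

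Four stronger readings are tempting, and the documents do not support them.
- *Most categories cannot be assessed.* The category comparison above shows otherwise.
- *The SAP departs from the protocol.* The protocol does not ask for counts by category.
- *The loss can be stated as a drop in the chance of detecting a difference.* That needs event rates and the share of events held by each term. The documents give neither, and the result would follow the assumed share. The SAP also plans counts and percentages for adverse events, not tests.
- *The eCRF already holds a category for every AESI.* This is stated only for serious AESIs and liver events.

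What the defence does not answer is the cardiac and cerebrovascular composite. The fatal-event table covers one component, and counting from a listing is not a prespecified summary.

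**Conclusion.** The point holds as a reporting gap of modest size. Of the SAP's six categories, one, the cardiac and cerebrovascular composite, has no obtainable count of men per arm from any planned table. Cystitis/UTI may be partly affected. Urinary retention, hypertension and neoplasms are largely readable elsewhere, and the liver category is shown indirectly through laboratory tables.

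This rests on the output list being complete for AESIs, on events being recorded as Protocol Section 8.4.6 directs, and on the organ-class assumption for neoplasms. Efficacy analyses and type I error are untouched. It is a cheap improvement worth making, not a flaw that undermines the safety analysis.

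**What to change.** In Tables 14.3.1.12 and 14.3.1.13, add one row per AESI category with n and % of men per arm, each man counted once per category, and nest the preferred terms beneath. Amend the layout sentence in SAP Section 7.1 to say so.

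Before unblinding, state how membership is decided: by the eCRF category or by a prespecified term list. If the eCRF category is chosen, first confirm that it is collected for nonserious AESIs. The rule should also say whether a fatal event outside the cardiac and cerebrovascular field enters the composite, and whether one event may belong to two categories. Reconcile the category list at the same time: Protocol Section 8.4.6 includes orthostatic hypotension, SAP Section 7.1 does not, and SAP Section 9 does not record the change.

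A risk difference with 95% CI per category is optional.

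The cost is one extra grouping level in two tables and a short membership rule. No new data are needed if a term list is used.

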4.3.5. Pre-existing and Baseline Hypertension

Pre-existing Hypertension will be assigned based on a search of a subject’s medical history for the presence (Yes) of any or absence (No) of all the following coded terms:

- Accelerated hypertension
- Diastolic hypertension
- Essential hypertension
- Hypertension
- Hypertensive crisis
- Hypertensive emergency
- Hypertensive heart disease
- Malignant hypertension
- Malignant hypertensive heart disease
- Secondary hypertension
- Supine hypertension
- Systolic hypertension

Baseline Hypertension will be assigned based on a subject’s baseline vital signs:

- Visit average SBP \geq 140
- Visit average DBP \geq 90

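### Two hypertension adverse-event tables select one preferred term, while the SAP defines pre-existing hypertension by 12 terms; an on-treatment event coded only to another term would be missing from those tables

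*SAP*

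**What the plan says.** SAP 7.1 plans hypertension TEAE summaries by pre-existing and by baseline hypertension, with this selection rule: "Hypertension TEAEs will be selected as any TEAE with preferred term of Hypertension". The matching outputs in SAP 11.2.1 are Tables 14.3.1.15 and 14.3.1.16, both on the safety set. The first is titled "Hypertension Treatment Emergent Adverse Events by Preferred Term, and Pre-Existing Hypertension".

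SAP 4.3.5 sets the pre-existing flag by searching medical history "for the presence (Yes) of any or absence (No) of all the following coded terms". The list has 12 entries. One is Hypertension; others include "Hypertensive emergency", hypertensive crisis, and accelerated and malignant hypertension. Baseline hypertension, the stratifier of Table 14.3.1.16, comes instead from blood pressure readings at baseline.

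SAP 7.1 also plans a listing of medical history and events before double-blind treatment, with terms "belonging to the standard MedDRA query of hypertension will be created".

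Protocol 8.4.6 tells sites to record an AESI of Hypertension, or Worsening Hypertension in a man with a history of it, when a blood pressure criterion is met or antihypertensive medication is started or increased. A separate AE of increased blood pressure is for cases where "an elevated blood pressure measurement is clinically significant but does not fulfill the above definition for hypertension".

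**The concern.** In Table 14.3.1.15 the event being counted and the factor that splits the table are both called hypertension but are defined differently, and the SAP gives no reason. A hypertensive emergency in a man's history puts him in the Yes stratum; the same term on treatment, with no separate event coded to Hypertension, does not count as a hypertension TEAE. Several of the terms left out describe severe forms. Table 14.3.1.16 has the same narrow event filter, although its stratifier does not use coded terms.

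Hypertension is a predefined AESI, and these are the only listed adverse-event tables split by hypertension status. The SAP treats that status as important elsewhere: pre-existing hypertension is a covariate in the blood pressure model (7.3.1) and an at-risk subgroup (7.3.1.1). A reader would take these two tables as the count of men with on-treatment hypertension in each stratum, and they may fall short of it.

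**Working it through.** The plan states no figure for this point, so there is none to reproduce. The check compares the rules, traces the outputs and then gives a scale.

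**1. Terms.** SAP 4.3.5 lists 12 terms. The rule in SAP 7.1 keeps 1, so 12 - 1 = 11 are outside it. A title that promises a display by preferred term has little meaning if only one term can appear, but that does not show which filter was intended.

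**2. Where an event coded to one of the 11 would appear.**

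| Output | Event included? |
|---|---|
| 14.3.1.15 and 14.3.1.16, hypertension TEAEs by hypertension status | No, unless the man also has an event coded to Hypertension |
| 14.3.1.2, all TEAEs by SOC and preferred term | Yes |
| 14.3.1.5 (Grade 3 and above), 14.3.1.8 (serious) | Yes, if it qualifies |
| 14.3.1.12 (AESI table), 14.3.1.20 (AESI listing) | Yes, if it meets Protocol 8.4.6 |

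The general tables are by preferred term and not by hypertension status. A man can appear under more than one term, so adding rows does not give the number of men with any hypertension event.

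**3. Worsening Hypertension.** Protocol 8.4.6 prescribes this wording for men with a history of hypertension. Neither document says which preferred term it codes to. If it codes to Hypertension, nothing is lost by this route. If not, the loss falls mainly in the pre-existing = Yes stratum.

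**4. Scale.** Inputs: 544 men per arm (SAP 1.2.4). The incidence p of a hypertension-type TEAE and the share s of affected men coded only to another term are assumptions; the documents give neither.

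Men missing per arm = 544 × p × s. Percentage shown = p × (1 - s).

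| p | Men affected | Missing at s = 0 | Missing at s = 5% | Missing at s = 10% |
|---|---|---|---|---|
| 2% | 10.9 | 0 | 0.5 | 1.1 |
| 5% | 27.2 | 0 | 1.4 | 2.7 |
| 10% | 54.4 | 0 | 2.7 | 5.4 |

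At p = 5% and s = 5% the tables would show 5% × 0.95 = 4.75% instead of 5.0%. The chance that at least one man is missing from an arm is then 1 - (1 - 0.0025)^544 = 74%. These shares do not model Worsening Hypertension coding elsewhere as a group; in that case s could be well above 10%.

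**The case against.** The strongest case against is that the rules serve different purposes. Medical history is not recorded under a scripted term, so a broad list suits a yes/no flag. On-treatment events have prescribed wording and numeric criteria, and any start or increase of antihypertensive medication triggers the AESI. A crisis treated that way should therefore also produce a record of Hypertension or Worsening Hypertension. Measured blood pressure is analysed independently of coding, including threshold analyses in men with pre-existing hypertension and in their complement (SAP 7.3.1.2).

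Much of this stands. It makes the loss conditional and probably small. It does not explain why one table uses two definitions of the condition, nor does it settle the coding of Worsening Hypertension. The threshold analyses use changes in readings and do not capture the medication criterion.

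A reader might go further than the documents allow in four ways:

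- **That on-drug hypertension, including its severe forms, is undercounted in the trial's reporting.** The narrow rule governs two tables, and the events remain visible in the outputs traced above.
- **That leaving out increased blood pressure is an error.** Protocol 8.4.6 deliberately places it outside its hypertension definition, so the SAP follows the protocol here.
- **That pre-treatment hypertension is counted more generously than on-treatment hypertension.** The 12 terms set a subgroup flag and the MedDRA query feeds a listing; neither is a pre-treatment event count set against an on-treatment one.
- **That the comparison between arms is biased.** The same filter applies to both arms, and nothing in the documents shows a differential effect.

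**Conclusion.** The point holds as an unexplained inconsistency confined to Tables 14.3.1.15 and 14.3.1.16. The mismatch of 1 term against 12 is certain from the text; that any man is actually missed is not. That requires an event coded only to one of the other 11 terms, or Worsening Hypertension coding to something other than Hypertension.

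Under the assumed ranges (2-10% incidence, 0-10% coded only elsewhere) the loss is 0 to about 5 of 544 men per arm, and the documents cannot narrow this. The kind of event that could drop out matters more than the number, since the list includes severe forms. The efficacy analyses are not affected. This is a limited improvement at almost no cost.

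**What to change.** In SAP 7.1, replace the single-term rule for Tables 14.3.1.15 and 14.3.1.16 with one pre-specified selection: either the 12-term list in SAP 4.3.5 or the hypertension AESI flag from Protocol 8.4.6. The list matches the stratifier of Table 14.3.1.15; the flag matches the predefined safety concept. Under either choice, state that events recorded as Worsening Hypertension are captured, and check this against the coded terms before unblinding. A separate row for increased blood pressure is optional.

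The cost is a sentence or two in the SAP and a change of term filter, with no new data. The counts may come out slightly higher than under the present rule. If the data are already unblinded, add the broader selection as a labelled supplementary table and record it in the study report, where SAP section 1 already requires changes to the final plan to be documented.
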